6.4.1 Potential Distant Spread of Toxin Adverse Events (applicable to BOTOX[®] studies only)

To assess possible distant spread of toxin (PDSOT), 40 MedDRA (version 17.0) preferred terms that may be associated with botulinum toxin effects have been identified. All AEs associated with PDSOT will be tabulated by SOC and treatment group; in addition, all PDSOT AEs will be listed by subject. The 40 terms are listed below.

MedDRA Preferred Terms Evaluated for Possible Distant Spread of Toxin

Cardiac Disorders	Nervous System Disorders	
Bradycardia	Bulbar palsy	
	Cranial nerve palsies multiple	
Eye Disorders	Cranial nerve paralysis	
Accommodation disorder	Dysarthria	
Diplopia	VIIth nerve paralysis	
Extraocular muscle paresis	Facial paresis	
Eyelid function disorder	Hyporeflexia	
Eyelid ptosis	Hypotonia	
Pupillary reflex impaired	Paralysis	
Vision blurred	Paralysis flaccid	
	Paresis cranial nerve	
Gastrointestinal Disorders	Peripheral nerve palsy	
Constipation	Peripheral paralysis	
Dry mouth	Speech disorder	
Dysphagia	Vocal cord paralysis	
Ileus paralytic	Vocal cord paresis	
Infections and Infestations	Renal and Urinary Disorders	
Botulism	Urinary retention	
Musculoskeletal and Connective Tissue Disorders Muscular weakness	Respiratory, Thoracic and Mediastinal Disorders	
	Aspiration Diaphragmatic paralysis Dysphonia Dyspnoea Pneumonia aspiration Respiratory arrest Respiratory depression Respiratory failure	

Reproductive System and Breast Disorders Pelvic floor muscle weakness

Note: The evaluation of events mapping to these terms will take into consideration the known mechanism of action of $BOTOX^{\textcircled{B}}$, the temporal relationship of the event (time to onset of the AE), the duration of the event, any re-challenge information if applicable, confounding factors that may include co-morbidities, past medical history, concomitant medications and other non-specific constitutional symptoms of a subject.

The list may need to be updated before database lock due to version change of the MedDRA.

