5.4 Treatment Allocation Ratio and Stratification

Patients will be randomly allocated (based on a randomization schedule, prepared by Allergan biostatistics) to BOTOX or placebo.

Study medication allocation will be performed using the interactive voice response system (IVRS) or the interactive web response system (IWRS).

For Cohorts 1-5, the allocation ratio for sentinel patients will be 1:1 BOTOX to placebo. The allocation ratio for subsequent patients will be 7:1 BOTOX to placebo. Two additional sentinel patients can be enrolled if requested by the DRC; further sentinel patients will be treated with BOTOX and will be in addition to the 10 planned patients within a cohort.

For Cohort 6, no sentinel dosing will occur. Twenty-four patients will be randomized at a ratio of 1:1 to receive either BOTOX or placebo. Patients who choose to participate in the open-label period will receive treatment with BOTOX.

There will be no stratification performed in the study.

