9.1 Definitions

9.1.1 Adverse Event

An adverse event is any untoward medical occurrence in a patient or clinical investigation subject administered a pharmaceutical product and that does not necessarily have a causal relationship with this treatment. An adverse event can therefore be any unfavorable and unintended sign (including an abnormal laboratory finding), symptom, or disease temporally associated with the use of a medicinal (investigational) product, whether or not related to the medicinal (investigational) product. In addition, during the screening period, adverse events will be assessed regardless of the administration of a pharmaceutical product.

Note: Adverse events must be collected once informed consent has been obtained, regardless of whether or not the patient has been administered study drug.

Adverse events will be assessed, documented, and recorded in the eCRF throughout the study (ie, after informed consent has been obtained). At each visit, the investigator will begin by querying for adverse events by asking each patient a general, nondirected question such as "How have you been feeling since the last visit?" Directed questioning and examination will then be done as appropriate. All reported adverse events will be documented on the appropriate eCRF.

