6.1.2 Administration of Study Treatment(s)

Patients will receive a single treatment administration during the study, consisting of 2 injections (each containing half of the total dose) of the assigned study medication to be delivered bilaterally (1 injection per side) to the bulbospongiosus muscle. Injection of the study medication will be performed using ultrasound guidance.

The following options are permitted either alone or in combination before treatment administration:

- No anesthesia
- Topical local anesthesia
 - Sterile local anesthetic topical preparation (eg, lidocaine cream) may be applied to the skin around the injection site
- Local anesthetic injections to skin
 - Sterile local anesthetic solution (eg, lidocaine solution) may be injected to the skin overlaying the injection site
- Sedation
 - If it is clinically indicated, may be administered to the patient at the investigator's discretion

Information on injection of study medication, including date, time of injection, number of injection sites, total volume injected and injection location will be provided in a data listing.

6.2 **Pre-Treatment Adverse Events**

Adverse Events with an onset date that is before day 1 of the randomized period of the study will be counted as pretreatment adverse events.

Adverse events will be coded from the verbatim text into MedDRA primary SOC and PT. Pretreatment AEs will be presented in descending order of incidence rate by the treatment group patient was randomized to for all randomized patients.

No statistical comparison will be performed.

A patient listing will be generated for pretreatment adverse events.

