6.4 Adverse Events

AEs will be coded from the verbatim text into PT and the primary SOC using MedDRA.

AEs are collected both for the screening/baseline period pretreatment (which are referred to as pretreatment AEs) and for the follow-up period after treatment is initiated (which are referred to as posttreatment AEs). A treatment-emergent adverse event (TEAE) is an adverse event with onset on or after the initiation of study treatment or an adverse event with onset prior to study treatment that worsened in severity or became serious after the initiation of study treatment. For the randomized period of the study, TEAEs are those with onset on or after the first study treatment, and prior to the study treatment for the open-label period, if applicable; for the open-label period, TEAEs are those with onset on or after the study treatment for the open-label period.

Three incidence rate tables are standard for summarizing all TEAEs:

- by descending order of incidence rate
- by primary SOC and PT
- by primary SOC, PT and severity

Number and percent of patients with TEAEs will be tabulated by relationship to study drug and study procedures. All treatment-related TEAEs, either study drug-related or study procedure-related will also be presented by descending incidence and by primary SOC and PT for each treatment group. Separate tables will be generated for study drug-related and study procedure-related TEAEs. TEAEs leading to study discontinuation will also be tabulated by primary SOC and PT for each treatment group.

No statistical comparisons will be made for any adverse event table.

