6.5 Serious Adverse Events

The number and percent of patients with serious TEAEs will be tabulated by treatment group for all serious TEAEs and treatment (study drug- or study procedure-, separately) related serious TEAEs by primary SOC and PT. Serious TEAEs will leading to study discontinuation will also be summarized by Primary SOC.

All serious adverse events and deaths will also be presented in a listing for each treatment group.

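### The distant-spread-of-toxin table in SAP 6.4.1 is not limited to treatment-emergent events and has no rule for events after open-label BOTOX

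*SAP*

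**What the plan says.** SAP 6.4.1 identifies 40 MedDRA preferred terms that may reflect botulinum toxin effects and sets one rule for the table: "All AEs associated with PDSOT will be tabulated by SOC and treatment group". It adds a by-subject listing of the same events. A note says that events will be evaluated in light of mechanism, time to onset, duration and confounders. The section names no study period and does not use the term TEAE.

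The surrounding text draws the distinctions that SAP 6.4.1 omits:

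- **What an AE is.** SAP 6.4: "AEs are collected both for the screening/baseline period pretreatment", and also for the follow-up after treatment. Protocol 9.1.1 starts collection early: "Adverse events must be collected once informed consent has been obtained".
- **Pretreatment events.** SAP 6.2 gives them their own definition, table and listing: "Adverse Events with an onset date that is before day 1 of the randomized period of the study will be counted as pretreatment adverse events".
- **The other tables.** SAP 6.4: "Three incidence rate tables are standard for summarizing all TEAEs". The relatedness and discontinuation tables in that section also use TEAEs. SAP 6.5: "The number and percent of patients with serious TEAEs will be tabulated by treatment group".
- **Periods.** The TEAE definition in SAP 6.4 separates the randomized period from the open-label period.
- **Open-label treatment.** Protocol 5.4, on Cohort 6: "Patients who choose to participate in the open-label period will receive treatment with BOTOX". This includes patients first randomized to placebo.
- **Columns.** SAP 2.1 analyzes the safety population by dose received. SAP 2.3 pools placebo patients from all cohorts into one group.

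**The concern.** The PDSOT table is the only table in the SAP dedicated to systemic toxin effect. An event that began before the first injection cannot be spread of injected toxin, yet the stated rule admits it. The window is not short: Protocol 8.3.1 allows up to 42 days of screening plus 28 days of washout, 70 days in all, and longer with sponsor approval. The list includes non-specific terms such as constipation, dry mouth, blurred vision and dyspnoea, which can have causes other than toxin.

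The second gap follows from the first. Because the period split exists only within the TEAE definition, a table that does not use that definition has no period split either. A Cohort 6 patient may receive placebo and then open-label BOTOX, and SAP 6.4.1 does not say which column holds an event after the second treatment.

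SAP 6.4 makes no statistical comparisons for AE tables, so the displayed counts are themselves the evidence. The groups are small enough for one misplaced patient to be visible.

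**Working it through.** **1. The section's own figure.** Counting the listed terms by organ class, in SAP order (cardiac, eye, gastrointestinal, infections, musculoskeletal, nervous system, renal, respiratory, reproductive, with reproductive placed last): 1 + 7 + 4 + 1 + 1 + 16 + 1 + 8 + 1 = 40. This reproduces the stated 40. The list is not in dispute; the event set is.

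**2. Event sets side by side.**

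| Table | Event set | Period split |
|---|---|---|
| SAP 6.2 pretreatment | Onset before day 1 of the randomized period | Not needed |
| SAP 6.4 incidence, relatedness, discontinuation | TEAEs | Yes, through the definition |
| SAP 6.5 serious events | Serious TEAEs | Yes, through the definition |
| SAP 6.4.1 PDSOT | All AEs | None stated |

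Since SAP 6.4 includes pretreatment events among AEs, a programmer following SAP 6.4.1 literally would include them.

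**3. Weight of one patient.** Inputs: 8 BOTOX and 2 placebo patients in each of Cohorts 1-5, and 12 and 12 in Cohort 6 (Protocol 3). Assumptions: enrollment is as planned and the table shows percent of patients, as its neighbors do.

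- BOTOX column for one of Cohorts 1-5, dose groups not combined: 1/8 = 12.5 percentage points.
- Pooled placebo: 5 × 2 + 12 = 22, so 1/22 = 4.5 percentage points.

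The documents give no background rate for these terms, so the expected number of pretreatment events cannot be computed.

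**4. Placebo patients who could later receive BOTOX.** Only Cohort 6 has an open-label period, so the ceiling is 12 of 22. The number continuing is not given. The range, which applies only if columns follow the randomized group:

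| Continuing (assumed) | Share of pooled placebo patients |
|---|---|
| 3 | 3/22 = 13.6% |
| 6 | 6/22 = 27.3% |
| 9 | 9/22 = 40.9% |
| 12 | 12/22 = 54.5% |

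If all 12 continue and each period lasts 12 weeks, 12/(22 + 12) = 12/34 = 35% of the follow-up in an unsplit placebo column would be after BOTOX.

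**5. After the change.** With the table limited to TEAEs and split by period, none of the 22 placebo patients contributes a post-BOTOX event to the placebo column of the randomized-period table.

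**The case against.** **Attribution.** A reader might infer that the SAP places placebo patients' events after open-label BOTOX in the placebo column. The documents do not say so. SAP 2.1 uses the dose received, and such a patient has received BOTOX. The TEAE definition in SAP 6.4 separates the periods, and the SAP amendment list says that SAP 6.4 was amended for open-label safety. The pooling rule in SAP 2.3 concerns combining placebo patients across cohorts. What stands is narrower: SAP 6.4.1 states no rule, and dose received does not settle the column for someone who has received both treatments. The open-label update is also incomplete elsewhere, since SAP 6.1.2 still describes a single treatment administration.

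**Direction.** A reader might also infer that the gap necessarily shrinks the BOTOX-placebo contrast. That is not shown. As an illustration only, assume a 2% background risk per 12 weeks, a 5% risk per BOTOX injection, all Cohort 6 patients continuing, and columns by randomized group:

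- Placebo column: (10 × 0.02 + 12 × (1 − 0.98² × 0.95))/22 = 5.7%, against 2% without the open-label period. With no toxin risk at all, the longer follow-up alone gives (10 × 0.02 + 12 × (1 − 0.98²))/22 = 3.1%.
- Cohort 6 BOTOX column: 1 − 0.98² × 0.95² = 13.3%, against 1 − 0.98 × 0.95 = 6.9%.
- Difference for Cohort 6: 13.3 − 5.7 = 7.6 points, wider than 6.9 − 2 = 4.9.
- Difference for a Cohort 1-5 BOTOX group at the same risk: 6.9 − 5.7 = 1.2 points, narrower than 4.9.

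None of these risks comes from the documents.

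**Other sources.** Treatment-emergent events with these terms also appear in the TEAE tables by organ class and preferred term. PDSOT events are listed by subject, and the note calls for time to onset to be weighed. The trial is an exploratory phase 2a study, and no test depends on this table. All of this stands and limits the harm: a careful reader can separate the events. It does not change which events the grouped table counts, or in which column.

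**Conclusion.** The point holds in two parts of different strength.

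The missing treatment-emergent restriction is established on the text. Read as written, SAP 6.4.1 presents pre-injection events as possible distant spread. One affected patient moves an uncombined Cohort 1-5 BOTOX column by 12.5 points and the pooled placebo column by 4.5 points, given planned enrollment and a table of percentages of patients.

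The open-label part is an omission. SAP 6.4.1 has no period or attribution rule, so misplacement is possible for up to 12 of 22 planned placebo patients if columns follow the randomized group. The documents do not establish that this will happen, how many patients will continue, or which way the contrast would move.

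The consequence is confined to the grouped PDSOT counts. The change should still be made, because this is the table to which a reader will turn for toxin spread and the correction is nearly free.

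**What to change.** In SAP 6.4.1, before database lock:

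1. Change the event set to *all treatment-emergent AEs associated with PDSOT*, using the SAP 6.4 definition. That definition already retains events that began before treatment and then worsened or became serious.
2. Tabulate the randomized period by treatment received, and the open-label period in a separate table under open-label BOTOX. This also settles the column for patients who had placebo and then BOTOX.
3. Keep pretreatment PDSOT events in the by-subject listing, flagged as pretreatment.

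Cost: a sentence or two in the SAP and one extra table shell. The treatment-emergent and period flags are already needed for the other AE tables, and no new data are collected.

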6.5 Serious Adverse Events

The number and percent of patients with serious TEAEs will be tabulated by treatment group for all serious TEAEs and treatment (study drug- or study procedure-, separately) related serious TEAEs by primary SOC and PT. Serious TEAEs will leading to study discontinuation will also be summarized by Primary SOC.

All serious adverse events and deaths will also be presented in a listing for each treatment group.

6.6 Clinical Laboratory Evaluations

Hematology and non-fasting clinical chemistry blood samples and urine sample are collected and processed by a central laboratory at screening, week 4 and week 12 for both the randomized period and the open-label period of the study. Measures collected are:

- Hematology: Hematocrit, hemoglobin, mean corpuscular hemoglobin, mean corpuscular hemoglobin concentration, mean corpuscular volume (MCV), platelets, red blood cell (RBC) count, RBC morphology, total white blood cell (WBC) count and differential (eg, neutrophils, bands, lymphocytes, monocytes, basophils, and eosinophils).
- Nonfasting serum chemistry: albumin, alkaline phosphatase, alanine transminase, aspartae transminase, bicarbonate, calcium, chloride, creatinine, creatine kinase, direct bilirubin, nonfasting glucose, indirect bilirubin, magnesium, phosphorous, potassium, sodium, total bilirubin, total cholesterol, total protein, urea nitrogen, and uric acid.
- Urine samples: clarity, color, bilirubin, blood, glucose, ketones, leukocyte esterase, nitrite, pH, protein, specific gravity, urobilinogen, microscopic sediment (WBCs, RBCs, casts, bacteria, crystals, and epithelial cells)

An urine culture and sensitivity will be analyzed by the central lab when the central lab urine analysis results are suggestive of a urinary tract infection (eg. Positive leukocyte esterase, nitrites, blood, or microscopic sediments such as WBCs, RBCs and/or bacteria) All clinical laboratory data analyses and presentations are to be expressed in the SI (Standard International) units.

Hematology, blood chemistry and urine analysis values will be summarized by visit with descriptive statistics. Change from study baseline (defined as the last assessment prior to study medication administration) will be summarized with descriptive statistics. For the

randomized period, baseline is the last assessment prior to the study medication of the randomized period of the study. For the open-label period, baseline is the last assessment prior to the study medication of the open-label period of the study. Within-group change will be evaluated by Wilcoxin Signed-rank test.

Laboratory values will be categorized as low, normal, and high according to the reference normal range. For each variable, cross-tabulations (shift tables) of low/normal/high values at study baseline will be compared to those at each post-treatment visit.

Listing of all laboratory data, as well as a patient-level listing of all abnormal (high/low) laboratory values will be provided.

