2.2 Clinical Hypotheses

BOTOX injected bilaterally into the bulbospongiosus muscle has an acceptable safety profile and shows an efficacy signal in comparison to placebo, as demonstrated by an increased IELT.

3. Study Design

This is a phase 2a, multicenter, randomized, double-blind, placebo-controlled, single treatment, pilot study followed by an open-label observation period, to assess a range of BOTOX doses for the treatment of male patients with PE. Patients will attend a minimum of 6 or 7 clinic visits and also have 1 or 2 telephone visits in the randomized period: screening, day 1 (treatment), day 2 (telephone visit for non-sentinel patients, clinic visit for sentinel patients, week 1 (telephone visit, and weeks 2, 4, 8, and 12/study exit). Partners will need to either attend a clinic visit or participate on a video conference during the screening period to provide informed consent and to receive training on measurement and recording of the IELT. For the open-label period, patients will have 2 clinic visits (weeks 4 and 12/study exit), along with 3 telephone visits (day 2, weeks 2, and 8).

For Cohorts 1-5, patients will be enrolled in cohorts of 10 patients. Within each cohort, 8 patients will receive BOTOX and 2 patients will receive placebo. For Cohort 6, patients will be enrolled into the randomized period in a 1:1 ratio, with 12 patients receiving BOTOX and 12 patients receiving placebo. Cohort 6 patients may choose to participate in the open-label period where they will receive BOTOX. For each treatment, patients will receive one injection of study medication delivered by ultrasound guidance bilaterally to the bulbospongiosus muscle.

Table 3–1 shows the planned dose escalation scheme; although, other interim doses may be recommended for investigation by the independent Data Review Committee (DRC) following data review.

Cohort	Total Dose	Sample Size	Total Patients in Cohort
1		N = 8	10
1	Placebo	N=2	10
2		N = 8	10
2	Placebo	N = 2	10
3		N = 8	10
	Placebo	N = 2	10
4		N = 8	10
	Placebo	N = 2	10
5		N = 8	10
	Placebo	N=2	10
6		N = 12	24
	Placebo	N = 12	24

Table 3–1 Planned Dose Escalation Scheme

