4.1 Number of Patients

Approximately 74 patients will be enrolled in the study.

For Cohort 6, approximately 24 patients will be enrolled at approximately 15 sites in the US and UK.

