2.1 Analysis Populations

There are 3 analysis populations defined in this study: modified intent-to-treat (mITT), per protocol (PP), and safety:

- The mITT population will be used to analyze all efficacy variables and summarize baseline characteristics. The mITT population is defined as all randomized patients that have received study medication and have both baseline and postbaseline IELT data available. Analyses on the mITT population will be based on the dose actually received by the patient.
- The PP population includes patients in the mITT population who have had no protocol deviations that affect the primary efficacy variable. The PP population will be used for analyzing the primary efficacy variable and summarizing baseline characteristics based on the dose received by the patient.
- The safety population includes all treated patients and will be used in the analysis of all safety data. Analyses on the safety population will be based on the dose received by the patient.

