2.3 Data Conventions

- A one-sided, alpha=0.1 significance level will be used for this study for treatment comparisons, i.e., treatment differences are considered significant if the 1-sided p-value of the test used in the comparison is less than or equal to 0.1.
- Data will be pooled across centers in all analyses. Placebo patients from different cohorts will also be pooled to form the placebo treatment group in all analyses.
- Day 1 is defined as the day of the first study medication administration. Study day is calculated as: Study day=visit date-day 1 date +1 for visits occurred after day 1 and study=visit date -day 1 date for visits occurred before day 1.
- The Medical Dictionary for Regulatory Activities (MedDRA) will be used to code all adverse events and medical history.
- Medications will be coded by the World Health Organization Drug Dictionary Enhanced (WHO DDE) preferred name for the medication's name and MedDRA for the medication's indication.
- All adverse events/medications with missing onset/stop dates will be identified and the missing dates will be imputed as follows:
 - a) For adverse event onset date: if day and month are missing but year is available then the imputed date would be January 1st of that year, or day 1 if they are in the same year. If day is missing but month and year are available then the imputed day will be the first day of the month or day 1 if they are in the same month and year.
 - b) For adverse event stop date: if day and month are missing but year is available then the imputed day will be December 31st of that year, or the study exit date if they are in the same year. If only day is missing but moth and year are available then the imputed day will be the last day of the month of the year, or the study exit date if they are in the same month and year.

- Data from unscheduled/re-test visits, excluding lab data, will also be treated the same way as scheduled visits, i.e., put in the visit window and decided by the visit day's distance to target day as which one to be used in the analyses.
- Weight and height will be presented with the metric system units and laboratory data will be presented with the Standard International (SI) units.
- Summary statistics for continuous/ordinal data include sample size (N), mean, standard deviation, minimum, median, and maximum and that for categorical data include sample size (N), frequency count and percentage.

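### SAP 6.6 tests laboratory change only within each group, so its p-values cannot separate a BOTOX effect from change shared by all arms and depend on group size

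*SAP*

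**What the plan says.** Laboratory samples are taken "at screening, week 4 and week 12 for both the randomized period and the open-label period of the study". SAP 6.6 then lists the output. "Change from study baseline (defined as the last assessment prior to study medication administration) will be summarized with descriptive statistics", and there are low/normal/high shift tables and listings. The only test is in one sentence: "Within-group change will be evaluated by Wilcoxin Signed-rank test". It sits directly after the baseline definitions for both periods, so it appears to cover both.

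Three other provisions fix the groups:
- SAP 2.1: "Analyses on the safety population will be based on the dose received by the patient".
- SAP 2.3: "Placebo patients from different cohorts will also be pooled to form the placebo treatment group in all analyses".
- Protocol Section 3, for Cohorts 1 to 5: "Within each cohort, 8 patients will receive BOTOX and 2 patients will receive placebo". Cohort 6 is randomized "with 12 patients receiving BOTOX and 12 patients receiving placebo".

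SAP 2.3 sets a one-sided 0.10 level for treatment comparisons. It sets no level for a within-group test. SAP 6.4 and 6.7 rule out statistical comparisons for adverse events and vital signs.

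**The concern.** The safety question in a controlled trial is whether laboratory values change more on BOTOX than on placebo. A signed-rank test on one group's change asks whether that group moved from its own baseline. Season, assay drift and regression to the mean can all produce such movement without any drug effect.

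Unequal group sizes add a second problem. The same underlying shift is more likely to reach significance in a large group than in a small one, so differences in p-value between groups may reflect sample size only. A shift shared by all arms can then look like a finding in one arm and not in another. A real BOTOX effect can go unseen if drift runs the other way.

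The protocol and SAP use the placebo contrast elsewhere. SAP 2.3 defines treatment difference as BOTOX minus placebo, and the Protocol Summary has questionnaire change compared for each dose group against placebo in its safety paragraph. Laboratory data alone receive p-values for a contrast that ignores the control.

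**Working it through.** **1. The plan's own figures.** No power or error figure is given for laboratory tests. The only power figures are in Protocol Table 7-1, for IELT. They reproduce with SD(log) = sqrt(ln(1 + CV²)) and a noncentral t at one-sided 0.10. For a 2-fold change, 12 versus 12 and CV 1, SD = sqrt(ln 2) = 0.833 and the noncentrality is 0.693 / (0.833 × sqrt(1/12 + 1/12)) = 2.04 on 22 df. Power is 76.4% against the printed 76%. All 27 rows agree within one percentage point. They do not bear on SAP 6.6.

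**2. Group sizes.** Pooled placebo is 5 × 2 + 12 = 22 (derived; not printed in the documents). Dose groups are 8 in each of Cohorts 1 to 5 and 12 in Cohort 6. The total is 5 × 10 + 24 = 74, as Protocol 4.1 states.

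**3. Chance that the within-group test is significant with no drug effect.** Assume each patient's change is normal with mean δ (drift common to all arms) and SD 1. The statistic is the sum of the ranks of |change| over positive changes, referred to its exact null distribution (100,000 simulated data sets per setting). The documents give no laboratory SD, so δ is varied.

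| Drift and level | n = 8 | n = 12 | n = 22 |
|---|---|---|---|
| 0.3 SD, two-sided 0.05 | 9% | 14% | 25% |
| 0.5 SD, two-sided 0.05 | 19% | 32% | 58% |
| 0.8 SD, two-sided 0.05 | 43% | 67% | 93% |
| 0.5 SD, one-sided 0.10 in the direction of drift | 50% | 61% | 83% |

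**4. What the pattern across arms looks like.** Take 0.5 SD at two-sided 0.05 and treat arms as independent.
- Placebo significant and one given 8-patient arm not: 0.58 × 0.81 = 47%. The reverse: 0.42 × 0.19 = 8%.
- Placebo significant and no BOTOX arm significant (five arms of 8, one of 12): 0.58 × 0.81⁵ × 0.68 = 14%.
- At least one BOTOX arm significant: 1 − 0.81⁵ × 0.68 = 76%.

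**5. Masking.** A drug effect of +0.5 SD with a drift of −0.5 SD gives a net change of 0. The test is significant only 4% of the time at n = 8 or 12.

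**6. The controlled contrast.** The expected difference in change is (δ + effect) − δ = effect, so drift cancels. A rank-sum test against 22 placebo patients, with 0.5 SD drift and no drug effect, is significant 4.4% (n = 8) and 4.7% (n = 12) of the time at two-sided 0.05. For a true effect of 0.8 SD over placebo, power is 42% and 55%. The approximate 95% half-width for a difference in mean change is 2.05 × sqrt(1/8 + 1/22) = 0.85 SD at n = 8 and 2.04 × sqrt(1/12 + 1/22) = 0.73 SD at n = 12.

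**7. Volume.** SAP 6.6 lists 14 numeric haematology, 21 chemistry and 2 numeric urine measures (pH, specific gravity), 37 in all. Over two visits of the randomized period and seven groups that is 37 × 2 × 7 = 518 tests. At a nominal 5% about 26 would be false positives. Allowing for the test's discreteness (true sizes 3.9%, 4.3% and 4.6% at n = 8, 12 and 22), it is 74 × (5 × 0.039 + 0.043 + 0.046) = 21.

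**The case against.** The case for leaving the plan alone is that this is an exploratory pilot and no stated decision depends on these p-values. Investigators judge abnormal results clinically (Protocol 6.3.2 and 6.3.3), and the data review committee's analyses have their own plan (SAP introduction). That stands, and it limits the importance of the point.

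A reader might infer that the p-values will point the wrong way, with placebo significant and BOTOX not. The documents do not support that. Step 4 puts the pattern at 47% against a single 8-patient arm and 14% across all arms, and some BOTOX arm is significant more often than placebo (76% against 58%).

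A reader might also infer that the plan leaves no way to tell a drug effect from time. That is true of the test but not of the whole plan. Descriptive change, shift tables and listings still allow an informal comparison with pooled placebo, although SAP 6.6 does not say they are shown by treatment group, as SAP 6.7 does for vital signs.

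The group sizes are not certain. Doses are redacted and the committee may repeat cohorts (Protocol 3.2). If Cohort 6 shares a dose with one earlier cohort, that group has 8 + 12 = 20 patients and its rate at 0.5 SD is 54% against 58% on placebo. If it shares with two, the group has 28 and placebo is no longer the largest. The contrast remains uncontrolled whatever the sizes.

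Finally, a placebo contrast does not reduce multiplicity. Six dose groups give 37 × 2 × 6 = 444 intervals, and at 95% about 22 would exclude zero by chance.

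**Conclusion.** The point holds in a limited form. The only planned laboratory inference is uncontrolled, and whether it reaches significance depends on group size as well as on any real change. On the planned sizes, a common drift of 0.3 to 0.8 SD is significant about two to three times as often on placebo as in an 8-patient dose group at two-sided 0.05. At one-sided 0.10 the ratio at 0.5 SD falls to 83/50, about 1.7. The p-values are likely to mislead; it does not follow that they must.

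The figures rest on assumed drift sizes, an assumed test level, normal changes, complete data and no dose repeated across cohorts. The objection to the contrast itself needs none of these. The gain from changing it is a valid comparison, with little sensitivity at 8 per dose. The importance is minor to moderate.

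**What to change.** In SAP 6.6, for the randomized period:
- Delete the within-group signed-rank tests.
- Report change from baseline by treatment group, and for each analyte and visit the difference in change between each dose and pooled placebo with a confidence interval. Use ANCOVA on baseline, or a Hodges-Lehmann estimate where the data are skewed.
- Label these results descriptive and unadjusted for multiplicity.
- State that the shift tables are shown by treatment group.

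For the open-label period, which has no concurrent placebo, present change descriptively without p-values.

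The cost is SAP wording and table shells; data collection and conduct are unaffected. The price is wide intervals at 8 per dose and about as many intervals as there were tests.
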